#### **Algorithm to flag whether a selected record is “Prior”, “Present”, or “Post” relative to the first dose date:**

- d) the start and stop dates of the selected record are not completely missing (ie, at least year is known) or the start date is not missing and record is ongoing. The completed start or stop dates will be used to compare with the first dose date whenever possible. Otherwise, the month and year (or year alone if month is not recorded) of the start or stop dates will be used to compare with the first dose date when the start or stop date of the selected record is incomplete.
  - i) The record is flagged as “Prior”, if the stop date is before ( $<$ ) the first dose date;
  - ii) The record is flagged as “Present”, if the start date is on or before ( $\leq$ ) the first dose date and the stop date is on or after ( $\geq$ ) the first dose date, or the selected record is marked as ongoing and the start date is on or before ( $\leq$ ) the first dose date;
  - iii) The record is flagged as “Post”, if the start date is after the first dose date;

- e) the start date of the selected record is completely missing. We assume that the start date is before the first dose date, the stop date (or the month and/or year of the stop date, if stop date is incomplete) will be used to determine whether the selected record is “Prior” or “Present” as follows.
  - i) The record is flagged as “Prior”, if the stop date is before (<) the first dose date or the stop date is completed missing and the record is not marked as ongoing.
  - ii) The record is flagged as “Present”, if the stop date is on or after ( $\geq$ ) the first dose date or the selected record is marked as ongoing.
- f) the start date of the selected record is before (<) the first dose date, but the stop date is completely missing and the record is not marked as ongoing. We assume that the end date is before the first dose date, the record is flagged as “Prior”.
- g) the start date of the selected record is on or after the first dose date, but the stop date is completely missing and the record is not marked as ongoing. This is a data issue, should be queried first. However, this record is flagged as “Present” if the start date is on the first dose; this record is flagged as “Post” if the start date is after the first dose.

#### 40) LDL: Conversions between 2nd and 3rd generations

LDL was analyzed by 2 different assays in the study: 2nd generation (including RCT2394, RCT2312, and RCT2811) and 3rd generation (RCT3870). Samples collected at earlier visits were analyzed using LDL 2nd generation assay. Samples collected at later visits were analyzed using LDL 3rd generation assay. The conversion formulas are as follow:

$$\text{2nd Gen (mmol/L)} = (\text{3rd Gen} - 0.0626)/0.882$$

$$\text{3rd Gen (mmol/L)} = (0.882 \times \text{2nd Gen}) + 0.0626$$

For this analysis, since LDL samples were analyzed by 2nd generation assay at Baseline, we only requested conversion from 3rd generation to 2nd generation.

For the analysis of change from baseline in fasting direct LDL: the sample analyzed by LDL 3rd generation assay will be converted to 2nd generation as a new record with test codes of LIP.LDL.00.02 in raw data. During ADaM stage, a derived parameter code (FLDL2) for “Fasting LDL Cholesterol 2ND GEN Combined” will be generated to pool the records from both original (including test codes RCT2394, RCT2312, and RCT2811) and converted (LIP.LDL.00.02) 2nd generation results to calculate the change from baseline in fasting direct LDL.

For the analysis of toxicity grade for fasting direct LDL: toxicity grade will be based on the Gilead grading results (ie, toxgrg) from original values before conversion. In another words, during ADaM stage, a derived parameter code (FLDLTOX) for “Fasting LDL Cholesterol for Toxicity” will be generated to pool the records from 2nd generation (including RCT2394, RCT2312, and RCT2811) and 3rd generation (ie, RCT3870) to derive treatment-emergent toxicity grades, maximum postbaseline toxicity grades, etc.

41) A subject is currently taking abacavir if the ingredient in the ARV form (variable INGRED) contains the substring “ABC” at baseline. Similarly, a subject is considered currently taking indinavir or lopinavir if the abbreviation contains the substring “IDV” or “LPV”.

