#### 7.2.2.1. Treatment-Emergent Laboratory Abnormalities

Treatment-emergent laboratory abnormalities are defined as values that increase at least one toxicity grade from baseline at any time post-baseline up to and including the date of last dose of study drug plus 30 days for subjects who permanently discontinued study drug. If the relevant baseline laboratory data are missing, then any abnormality of at least Grade 1 will be considered treatment emergent.

For serum glucose, fasting glucose and nonfasting glucose are graded based on different grading criteria as specified in the protocol. Treatment-emergent laboratory abnormalities will be summarized for fasting glucose. Since nonfasting glucose was not assessed at baseline, the maximum postbaseline grade instead of treatment-emergent laboratory abnormalities will be summarized.

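### Treatment-emergent LDL grades set a 2nd-generation baseline against unconverted, lower-reading 3rd-generation follow-up values, so they are under-counted wherever the two assays differ.

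*SAP*

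**What the plan says.** SAP Appendix 5, item 40 states that two LDL assays were used. Earlier samples were run on the 2nd-generation assay. For the rest, "Samples collected at later visits were analyzed using LDL 3rd generation assay". It gives a pair of conversion formulas in mmol/L and fixes the direction of conversion: "since LDL samples were analyzed by 2nd generation assay at Baseline, we only requested conversion from 3rd generation to 2nd generation".

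The two LDL analyses are then handled differently:

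- **Change from baseline.** Here "the sample analyzed by LDL 3rd generation assay will be converted to 2nd generation as a new record", and the converted and native 2nd-generation results are pooled as parameter FLDL2.
- **Toxicity grade.** Here "toxicity grade will be based on the Gilead grading results (ie, toxgrg) from original values before conversion". Unconverted results from both assays are pooled as FLDLTOX "to derive treatment-emergent toxicity grades, maximum postbaseline toxicity grades, etc".

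SAP section 7.2.2.1 gives the definition that these grades feed: "Treatment-emergent laboratory abnormalities are defined as values that increase at least one toxicity grade from baseline at any time post-baseline". Section 7.2.2.2 plans summaries of treatment-emergent abnormalities overall and by Part. Section 7.2.2 grades by the protocol criteria, and Protocol Appendix 4 has a single set of adult fasting LDL limits: Grade 1 from 3.35 to 4.15 mmol/L, Grade 2 above 4.15 to 4.92, and Grade 3 above 4.92. Neither document gives assay-specific limits, a reason for grading unconverted values, or a sensitivity analysis of grades on a common scale.

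**The concern.** A treatment-emergent grade is a within-subject contrast with baseline, just as a change from baseline is. The SAP accepts that raw values from the two assays cannot be subtracted from one another, yet it lets their grades be compared. If the later assay reads lower, a real rise across a grade limit can be hidden by the change of assay.

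Safety and tolerability are a secondary objective, and fasting lipids are scheduled at baseline, Week 24 and Week 48. The study has one arm, so no control group passes through the same assay change and shows the shift. The grade table could then disagree with the converted change-from-baseline table in the same report, and the reader would not see why.

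**Working it through.** **Inputs from the documents.** Conversion formulas, baseline assay and grading rule: SAP Appendix 5, item 40. Grade limits 3.35, 4.15 and 4.92 mmol/L: Protocol Appendix 4. Definition of treatment-emergent: SAP 7.2.2.1. Fasting lipid visits: SAP 1.2. Planned size of 64 subjects: SAP 1.3.

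**Step 1: the SAP's formulas.** 3rd = 0.882 × 2nd + 0.0626, and 2nd = (3rd − 0.0626)/0.882. Applying one and then the other returns 3.35, 4.15 and 4.92 exactly, so they are true inverses.

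**Step 2: direction.** 3rd − 2nd = 0.0626 − 0.118 × 2nd. This is negative once 2nd exceeds 0.0626/0.118 = 0.53 mmol/L, far below the lowest graded value.

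**Step 3: the limits on the baseline scale.** A 3rd-generation reading of t corresponds to (t − 0.0626)/0.882 on the 2nd-generation scale.

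| Grade limit t (mmol/L) | 2nd-generation equivalent needed | Excess over t |
|---|---|---|
| 3.35 (Grade 1) | 3.727 | 0.377 |
| 4.15 (Grade 2) | 4.634 | 0.484 |
| 4.92 (Grade 3) | 5.507 | 0.587 |

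**Step 4: two examples on the 2nd-generation scale.**

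- Baseline 3.2 (Grade 0), later 3.6 (Grade 1), is treatment-emergent. On the 3rd-generation assay the later sample reads 0.882 × 3.6 + 0.0626 = 3.238, which is Grade 0 and is not counted.
- Baseline 4.0 (Grade 1), later 4.5 (Grade 2), is treatment-emergent. The later sample reads 0.882 × 4.5 + 0.0626 = 4.032, which stays Grade 1 and is not counted.

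**Step 5: does the choice of common scale matter?** Take one comparison of a 2nd-generation baseline with a 3rd-generation follow-up. Converting the follow-up up to the 2nd-generation scale can only raise its grade. Converting the baseline down to the 3rd-generation scale can only lower the baseline grade. Either way, the mixed comparison can lose a treatment-emergent grade but not add one.

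**Step 6: illustration of size.** The following are assumptions, not document figures: baseline LDL normal with mean 3.0 and SD 0.8 mmol/L, SD of change 0.45, and two follow-up visits with independent changes. Four million simulated subjects; percentage with any treatment-emergent LDL grade:

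| True mean change | All on 2nd-generation scale | All on 3rd-generation scale | As planned, only Week 48 on 3rd | As planned, both visits on 3rd |
|---|---|---|---|---|
| 0 | 24.5% | 16.9% | 16.5% | 6.3% |
| +0.3 mmol/L | 44.8% | 32.7% | 33.8% | 17.4% |

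When only Week 48 changed assay, the subject-level total lies clearly below the all-2nd-generation figure but close to the all-3rd-generation figure (33.8% against 32.7% with a rise). The Week 24 comparison is then a clean 2nd-generation one. The result in step 5 therefore applies to each mixed comparison; it does not say that every subject-level total falls below the all-3rd-generation total.

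**Step 7: range over other assumptions.** With baseline mean 2.8 to 3.3, SD 0.8 to 0.9, SD of change 0.35 to 0.5 and mean rise 0 to 0.4 mmol/L, the expected number among 64 subjects is about 10 to 36 on the 2nd-generation scale. It is about 7 to 29 if only Week 48 used the 3rd-generation assay, and about 2 to 17 if both visits did.

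**The case against.** The best defence is that grading the reported result against the protocol's fixed limits is a deliberate, openly stated choice. A converted value is a regression prediction, and the SAP gives no conversion error, so replacing observed grades with predicted ones has a cost. This stands as a reason to keep grades on reported values visible. It does not justify the treatment-emergent flag, which is a derived contrast; for the parallel contrast the SAP itself requires conversion.

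The consequence is also limited. This is one laboratory parameter in a descriptive study without formal testing. Adult LDL has no Grade 4. Numeric change in LDL is converted and would still show a rise. All of this stands, and it bears on priority rather than on whether the rule is wrong.

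A reader might infer more than the documents support, in four ways:

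- **That most abnormalities are lost.** With a single follow-up visit on the 3rd-generation assay, the assumptions of step 6 give 14.3% falling to 3.3%. That is a worst case. The SAP counts an increase at any post-baseline time, two fasting visits are scheduled, and the documents do not say that all follow-up samples used the newer assay.
- **That the rule creates an apparent LDL improvement.** A treatment-emergent table counts only grade increases, so it cannot display improvement, and the change-from-baseline analysis that could is converted.
- **That the two LDL tables must contradict each other.** They are different summaries. They can disagree; whether they do depends on the data.
- **That maximum postbaseline grade is under-counted in the same firm sense.** That summary makes no comparison with baseline, and the documents do not say which assay is nearer the truth. The under-count there holds only relative to the 2nd-generation scale.

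**Conclusion.** The point holds for treatment-emergent LDL grades wherever a 2nd-generation baseline is compared with a 3rd-generation follow-up. The mismatch and its direction follow from the SAP's own rule and formula and need no assumption about LDL levels. The effective limits are 0.38 to 0.59 mmol/L higher for the follow-up sample than for the baseline sample. For each such comparison the loss is one-directional against either common scale. Subjects measured only on the 2nd-generation assay are unaffected.

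The size cannot be determined, because the documents give neither the changeover date, nor the share of follow-up samples on the newer assay, nor the LDL distribution. Under the assumptions of step 6, and relative to the 2nd-generation scale, about a quarter to a third of subjects with a treatment-emergent grade are missed if only Week 48 changed assay (33.8/44.8 = 0.75; 16.5/24.5 = 0.67). If both visits did, about 61% to 74% are missed (17.4/44.8 = 0.39; 6.3/24.5 = 0.26). The primary endpoint, adverse events and numeric LDL change are not touched. It should be corrected because the bias is known, runs one way and is nearly free to remove.

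**What to change.** In SAP Appendix 5, item 40, derive the LDL baseline grade, post-baseline grades and treatment-emergent flag from FLDL2, the combined 2nd-generation parameter already created for change from baseline. Keep the FLDLTOX grades on reported values in the listings and, if wanted, in a labelled supplementary table. Report the number of Week 24 and Week 48 samples on each assay, so that a reader can see how many comparisons were affected. State that maximum postbaseline grade depends on the scale chosen, and name that scale in the table.

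The cost is one programming change with no new data. More LDL abnormalities are likely to be reported, and grades for 3rd-generation samples will rest on converted values whose conversion error the SAP does not give; a footnote should say so.
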